For all variables, descriptive statistics will be calculated, including means, standard deviations, medians, and interquartile ranges for continuous variables and frequency counts and percentages for categorical variables. Data will be examined for skewness, outliers, and systematic missing data. Transformations will be undertaken as needed. Comparisons of demographic and baseline variables will be obtained by treatment group.

D.6.4.1 SA 1 Analysis Plan: To determine if REDvent acute and/or weaning phase protocols can shorten the duration of weaning from MV (Primary outcome).

Primary analysis and sample size: The primary outcome for this aim is weaning duration. Because we seek to understand whether REDvent-acute and/or REDvent weaning have an independent effect on length of weaning, we propose a sample size to adequately power 3 separate comparative analyses: **(a)** REDvent-acute versus Acute Phase control **(b)** REDvent-weaning phase versus Weaning Phase control **(c)** REDvent both phases versus control both phases. We expect up to 12% mortality before the first SBT based on our Preliminary Data. These patients will not be included in the analysis for the primary outcome. From our pilot data (REDvent in both acute and weaning phases), the duration of the weaning phase in the intervention arm was 2.2 days, compared to 4 days in historical controls with a standard deviation of 2.1 days in the intervention arm and 2.8 days in the historical controls.

[figure not shown]

Figure 8: Power curve for a 1 day reduction in weaning

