Additional details are also available in the published study protocol.² Baseline characteristics at the time of randomization will be computed for each treatment group (REDvent and usual care) and within each phase (Acute and Weaning). For all analyses, assumptions for data distribution will be assessed, and normalizing transformations of the data or nonparametric analysis will be performed as necessary. The mean and standard deviation will be reported for normally distributed continuous variables, and the median and interquartile ranges will be reported for non-normally distributed continuous variables. Given this is an RCT, we anticipate balanced baseline characteristics. To evaluate this, we will calculate effect sizes for measures of central tendency (Cohen d, Cramer v) across groups. For non-parametric

variables, effect sizes defined for the Mann-Whitney U will be calculated to produce r . For frequency counts and percentages the rate ratio will be evaluated to calculate the effect size. Variables that have more than a small effect size ($d > 0.2$, $v > 0.01$, or $r > 0.1$, categorical effect size >1.2) indicate potential imbalances in baseline characteristics between groups. These variables will be included in sensitivity analyses after the primary ITT analyses are performed or included as covariates using multivariable models.

Retention, adherence, and missing data will be compared across groups. High levels of missing data are not anticipated given the nature of the study. If the missing data are determined to be related to the outcome (not missing at random) or related to group or a covariate (missing at random), we will explore the impact of these biases in sensitivity analyses after the primary ITT analyses using multiple imputation processes. Our primary approach to imputing missing data is the Markov Chain Monte Carlo (MCMC) simulation. Statistical Analysis Software (SAS) procedures will be used.

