The analytic approach for secondary aims and outcomes such as mortality and ventilator free days will follow those described above. For categorical data, a χ^2 or Fisher's exact test will be used to compare difference between groups. Logistic regression will be used to assess binary outcomes, and a multinomial/ordinal logistic regression will be used for categorical outcomes (> 2 categories) while adjusting for covariates. To assess the association between 2 continuous variables, a Pearson or Spearman correlation will be used, and analysis of covariance (ANCOVA) will be used to adjust for covariates. Generalized Estimating Equations (GEE) or mixed effect models will be used when necessary to analyze repeated measures. Because of the physiologic nature of the study with a Phase II design,

multiple comparisons adjustment is not planned for secondary outcomes. Analyses will be performed using the appropriate recent version of the SAS statistical software (SAS Institute Inc., Cary, NC).

In order to increase precision around the effect estimates for the primary and secondary aims and to reflect the stratified sampling, all analyses are adjusted for block randomization variables.³ For acute phase these are age group (infant, child, and adolescent) and whether or not the subject was immunocompromised. For the weaning phase this is acute phase randomization grouping and age group. In addition, variables thought to be potential confounders on the relationship between intervention and outcome with large differences between groups (standardized effect sizes as detailed above) will also be included in all adjusted analyses. Unadjusted analyses will be presented to summarize data; all primary and secondary outcomes will present adjusted analyses controlling for age category, immunosuppression and imbalanced baseline variables. Potential confounders will be assessed for multicollinearity and if present, the confounder with the highest biological plausibility to impact the effect of the intervention on the outcome will be selected for inclusion as a model covariate.

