After the first 75 patients were enrolled in the study a new milestone accrual plan was created to account for the increase in the percentage of patients meeting the primary outcome. Previously, it was assumed 20% of patients would not meet the outcome, however, data after 75 patients revealed this was 13% and the total sample size requirement was adjusted down from 300 to 276 patients. The number of patients targeted per group to meet the primary outcome was unchanged, at 120 per group. This updated milestone accrual plan was reviewed and accepted by the NLHBI and DSMB.

January 2023 - Change in primary analysis for length of weaning

Blinded, non-inferential summary statistics and distributions were assessed for the length of weaning outcome by the primary statistician as part of the data cleaning process. It was revealed that length of weaning might not be optimally analyzed as a continuous variable because SBTs were conducted once a day, with most patients passing their SBT within the first three days. In addition, enrollment had been affected by the COVID-19 pandemic and a new milestone accrual plan was requested by the NHLBI. As the observed distribution appeared more count-like, the primary analysis model was changed to Poisson or Negative binomial regression to better fit the data and satisfy assumptions. This decision was made by the senior biostatistician who was blinded to the randomization groups.

The sample size was re-estimated based on a minimum detectable difference for a reduction in the number of weaning days in the REDvent-acute vs. usual care-acute group using negative binomial regression. This yielded a minimal sample size of 230 patients to detect a reduction of 0.36 to 0.75 days when usual care had an average number of weaning days between 1 and 4, respectively with a power of 80%. This estimate of 230 patients accounted for the 13% loss in those meeting the primary outcome. This updated sample size estimate was reviewed and accepted by the NHLBI and DSMB. Based on this, the milestone accrual plan was revised, and enrollment was planned to continue through March 2024 with a target sample size between 230-276.

May 2024 – Change in primary analysis for length of weaning and PiMax

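### The final SAP's Cramer's v cut-off for baseline imbalance (0.01) is ten times stricter than the d and r cut-offs beside it, and the SAP does not say whether v or the rate ratio governs categorical variables

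*Combined protocol and SAP*

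**What the plan says.** In the final SAP (July 2024), the baseline-characteristics paragraph of the Statistical Analysis Plan section first sets the population: "Baseline characteristics at the time of randomization will be computed for each treatment group". It then names the measures. For the first group, "we will calculate effect sizes for measures of central tendency (Cohen d, Cramer v) across groups". Non-parametric variables get the Mann-Whitney r. For the rest, "For frequency counts and percentages the rate ratio will be evaluated to calculate the effect size". A variable is marked as potentially imbalanced if it has "more than a small effect size ($d > 0.2$, $v > 0.01$, or $r > 0.1$, categorical effect size >1.2". Such variables go either to sensitivity analyses or into multivariable models as covariates. The Fall 2019 SAP has the same cut-offs, so 0.01 is not a late change, and its appearance in both versions makes a text-extraction fault unlikely.

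The covariate paragraph of the final SAP refers back to these effect sizes. It brings into all adjusted analyses "variables thought to be potential confounders on the relationship between intervention and outcome with large differences between groups (standardized effect sizes as detailed above". It also adds a check: "Potential confounders will be assessed for multicollinearity and if present, the confounder with the highest biological plausibility". The adjusted results are the ones to be presented for primary and secondary outcomes.

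**The concern.** Four cut-offs share one label and so should describe roughly the same degree of imbalance. Three steps suggest that they do not.

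- **Value.** Beside d > 0.2 and r > 0.1, a v of 0.01 looks like a slip of one decimal place.
- **Scope.** The SAP groups v with Cohen's d under central tendency, although Cramer's v measures association between categorical variables. It gives counts and percentages to the rate ratio, and protocol section D.6.4 uses "frequency counts and percentages for categorical variables" as the summary for that type of variable. Both v and the ratio could therefore apply to the same variable.
- **Precedence.** The criteria are joined only by an *or*, and no sentence ranks them.

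At stake is the traceability of covariate selection for the adjusted results. A threshold that flags nearly every categorical variable does no screening, and a threshold without a defined scope cannot be applied the same way twice.

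**Working it through.** **Inputs.** Cut-offs d > 0.2, v > 0.01, r > 0.1 and ratio > 1.2 (final SAP, baseline paragraph). Allocation 1:1 (final SAP, Randomization Strategy and Blinding). Number randomised: "target sample size between 230-276" (final SAP, January 2023 change). Weaning phase: 180 patients, 90 per arm (final SAP, power analysis). Prevalence of a binary baseline variable is an assumption, 5% to 50%, because the documents contain no baseline table for this trial.

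**1. Do the plan's cut-offs agree?** At 1:1 allocation r = d/√(d² + 4). With d = 0.2 this is 0.2/√4.04 = 0.0995, so d > 0.2 and r > 0.1 are one rule on two scales. With two arms v = √(χ²/N), and the Mann-Whitney r is Z/√N, so v and r share a scale. The inverse conversion is d = 2r/√(1 − r²):

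| cut-off | equivalent d |
|---|---|
| 0.01 | 0.020 |
| 0.10 | 0.201 |

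The value that matches the plan's own d and r is v > 0.1. The stated 0.01 is a factor of ten away.

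**2. What difference does v = 0.01 represent?** For a binary variable with pooled proportion p, v = |p₁ − p₂| / (2√(p(1 − p))), so the difference is 2v√(p(1 − p)).

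- p = 0.10: 2 × 0.01 × 0.3 = 0.6 percentage points (6 points at v = 0.1).
- p = 0.50: 2 × 0.01 × 0.5 = 1.0 percentage point (10 points at v = 0.1).

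With 138 per arm, 14 versus 13 patients gives p = 27/276 = 0.098 and v = (1/138)/(2 × 0.297) = 0.012. A split of 70 versus 68 gives v = (2/138)/(2 × 0.5) = 0.0145. Both exceed 0.01.

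**3. How often would chance alone trigger it?** To a first approximation, P(flag) = P(χ² on 1 df > N × cut-off²). At N = 240:

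- v > 0.01: 240 × 0.0001 = 0.024, P = 0.877.
- v > 0.1: 240 × 0.01 = 2.4, P = 0.121, the same as for d > 0.2 and for r > 0.1.

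Exact binomial enumeration, equal arms, no true imbalance, prevalence 5% to 50%:

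| N | v > 0.01 | v > 0.1 | d > 0.2 (two-sided t) |
|---|---|---|---|
| 230 | 83.4% to 93.2% | 12.4% to 13.7% | 13.1% |
| 240 | 83.2% to 93.0% | 11.9% to 13.5% | 12.3% |
| 276 | 82.4% to 92.1% | 9.5% to 10.4% | 9.8% |
| 180 (weaning) | 86.2% to 94.1% | 17.8% to 20.5% | 18.1% |

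**4. Does it matter whether v or the ratio governs?** With 120 per arm, no true imbalance, and the ratio taken as larger over smaller:

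| prevalence | v > 0.01 | ratio > 1.2 |
|---|---|---|
| 10% | 91.4% | 62.8% |
| 30% | 83.3% | 35.2% |
| 50% | 84.7% | 15.7% |

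The two rules give different lists. If any one criterion is enough, v > 0.01 makes the ratio nearly redundant: a ratio of 1.2 already corresponds to v of about 0.03 at prevalence 10% and 0.09 at 50%.

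**The case against.** The strongest reply is that the consequence is hypothetical. The SAP gives counts and percentages to the rate ratio, so on a plain reading v has no working role for categorical variables and 0.01 never bites. The only confounder named, in the PiMax text of the May 2024 change, is oxygenation index, which is continuous. A flag marks only a potential imbalance and may lead to no more than a sensitivity analysis. Entry into the adjusted models also requires that the variable be thought a confounder and pass the multicollinearity check. All of this stands and sets the size of the point. It does not remove it, because v > 0.01 remains a stated decision threshold and no sentence excludes it.

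A second reply is that the conversion from d uses the point-biserial r, whereas the SAP's r comes from the Mann-Whitney test. That is fair for d, but v against r needs no conversion, since each is a test statistic divided by √N.

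Two stronger readings are tempting and are not supported. A reader might infer that the covariate list cannot be recovered. The documents show only that it is absent here: the final SAP refers to a published protocol and to presented main results, neither of which is available for this review. A reader might also infer that the ratio catches an excess in one arm only. The SAP names no numerator and does not rule out dividing the larger by the smaller, so that is not established.

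**Conclusion.** The cut-off is wrong as written, and the scope of v is undefined. The inconsistency follows from the plan's own numbers at 1:1 allocation and needs no outside figure. The flag rates are conditional: they assume that v is applied to a binary variable, that there is no true imbalance, that arms are equal, and that prevalence is 5% to 50%. Even then 7% to 18% of balanced binary variables would escape the flag at N = 230 to 276.

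The point is minor. Blocking variables are adjusted for whatever the flag says. A reader might conclude that the reported models were filled with covariates flagged by chance. The documents do not support that, because nothing in them shows that v > 0.01 was applied. Confidence is high in the inconsistency. No effect on the results is claimed.

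**What to change.** In a dated correction to the final SAP:

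1. Change v > 0.01 to v > 0.1, or justify 0.01.
2. State that one metric, v or the rate ratio, governs categorical variables, and which was actually used.
3. If the ratio is kept, define it as larger over smaller, so that it does not depend on the choice of numerator.
4. Only if v > 0.01 was used to select covariates, disclose this and show the adjusted results under v > 0.1 as a sensitivity analysis.

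The cost is a short note, plus one sensitivity analysis in the last case. The correction is retrospective, since data cleaning ended in May 2024 and the models have been run, so the old figure should stay visible beside the new one. The downside is that some small categorical imbalances would no longer be flagged.

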Because the pre-specified plan was to use a negative binomial model, those findings have been presented in the main results, but because the model does not appropriately fit the data due to the highly influential outliers, the conclusions and abstract results reflect the more appropriate proportional odds model. This model was agreed upon by the study statistical team and DSMB statisticians in June 2024 at the final DSMB meeting.

PiMax was planned to be modeled with linear regression, with truncation of values >100. In the analysis, no transformation could satisfy the assumptions of linear regression, with poor model diagnostics and non-normality of residuals. PiMax was therefore modeled with the proportional odds model given the non-parametric nature of the data. No specific categories were created for PiMax, but instead it was treated as a rank-based variable with comparisons of ranks between groups, adjusting for blocking variables and confounders (oxygenation index). The model allowed us to compare the odds of a higher PiMax ranking for the REDvent vs. usual care groups. Table 1 has been revised and now presents the description of all outcome variables, initial planned analyses, and modifications to initial proposed analyses and the timing of those changes. In addition, since all outcomes are presented as adjusted analyses, Table 2 details the four main modeling approaches used in these analyses, and interpretation of the model intervention parameter estimates.

References

1. [name] RG, Smith LS, Zimmerman JJ, et al. Pediatric Acute Respiratory Distress Syndrome: Definition, Incidence, and Epidemiology: Proceedings From the Pediatric Acute Lung Injury Consensus Conference. *Pediatric Critical Care Medicine*. Jun 01 2015;16(5_suppl):S23-S40. doi:10.1097/PCC.0000000000000432
2. [name] RG, Hotz JC, Klein MJ, et al. A Phase II randomized controlled trial for lung and diaphragm protective ventilation (Real-time Effort Driven VENTilator management). *Contemp Clin Trials*. Jan 2020;88:105893. doi:10.1016/j.cct.2019.105893
4. Firth D. Bias Reduction of Maximum Likelihood Estimates. *Biometrika* 1993. p. 27-38.

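### Data judged not missing at random are sent to the same MCMC multiple imputation as missing-at-random data; the gap matters mainly for PiMax on the day of extubation, and it is minor

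*Combined protocol and SAP*

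**What the plan says.** The missing-data paragraph of the final SAP names two triggers in one sentence: "If the missing data are determined to be related to the outcome (not missing at random) or related to group or a covariate", the latter called missing at random. For either trigger, "we will explore the impact of these biases in sensitivity analyses after the primary ITT analyses using multiple imputation processes". It then names the method, "Our primary approach to imputing missing data is the Markov Chain Monte Carlo (MCMC) simulation", and adds that "Statistical Analysis Software (SAS) procedures will be used". The Fall 2019 SAP has the same text. Neither SAP lists the variables in the imputation model, and neither names a delta-adjusted, pattern-mixture, selection-model or tipping-point analysis.

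Four other places bear on the point:

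- **Distributions.** The SAP has a general safeguard: "normalizing transformations of the data or nonparametric analysis will be performed as necessary".
- **PiMax.** The May 2024 section reports that for PiMax "no transformation could satisfy the assumptions of linear regression, with poor model diagnostics and non-normality of residuals", and moves it to a rank-based proportional odds model. Table 1 restricts PiMax on the day of extubation to children who met the primary outcome. It excludes only those who died within 24 hours of extubation or were still intubated at 90 days.
- **End of measurement.** Protocol D.3.13 stops study interventions and daily measurements for a child who has not passed an SBT by day 28 after enrollment. Table 1 likewise says SBTs stop after the 28-day intervention, while extubation is followed to 90 days.
- **Length of weaning.** Table 1 settles most absent primary outcomes by rule: no SBT attempted, excluded; never passed and died within 24 hours of extubation, excluded; still intubated at 90 days, set to 90.

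**The concern.** A sensitivity analysis for data not missing at random has to let the unseen values differ from the seen ones in a way the observed data do not predict. Standard MCMC multiple imputation does the opposite: it draws missing values from a normal model fitted to the observed data, on the premise that those data are enough to predict them. This is a general property of the method; the SAP does not discuss it. If the premise fails, the imputed estimate stays close to the complete-case estimate, and that agreement can be reported as reassurance.

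The normal model is also a poor match for the outcomes. In 2024 both length of weaning and PiMax were moved to ordinal models because of poor fit, but the imputation text was left as it was.

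PiMax is the primary physiologic outcome (protocol C.3.2), and its day-of-extubation value can be absent for a reason tied to slow recovery. Table 1 has no rule for that absence.

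**Working it through.** The SAP states no missing-data figure, so there is nothing of its own to reproduce.

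**1. Where PiMax can be missing by design.** Eligible for PiMax on the day of extubation: children who met the primary outcome, with extubation possible up to day 90 (final SAP, Table 1). Measured: by airway occlusion before SBTs (protocol D.4.2), with measurement ending at day 28 for children who have not passed (D.3.13). A child extubated between day 28 and day 90 without having passed an SBT is therefore eligible but has no scheduled value. Measurements also stop after ECLS or removal of the esophageal catheter (D.3.14).

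The documents do not count these children. As a planning guide only, D.6.4.2 expects 90% of 240 to pass within 28 days of weaning randomization, which leaves 0.10 × 240 = 24. That number also holds deaths, children extubated earlier without a pass and children still ventilated at 90 days, and its clock starts later than enrollment. The January 2023 note that most children passed within three days points to fewer.

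**2. What normal-model imputation does when missingness depends on the outcome (weaning).** Inputs from protocol D.6.4.1: mean 2.2 days for REDvent and 4 days for historical controls, with a "standard deviation of 2.1 days in the intervention arm and 2.8 days in the historical controls". Assumed: lognormal outcomes, 120 per arm, 1,000 runs, 10 imputations, no auxiliary variables, and all missing values in usual care, chosen with probability proportional to the square of the value. With one incomplete variable, MCMC amounts to posterior draws from a normal regression on arm. Differences are REDvent minus usual care, in days:

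| Missing overall | Full data | Complete case | Normal imputation | Log-scale imputation | Normal imputation, +4 days |
|---|---|---|---|---|---|
| 1% | -1.79 | -1.71 | -1.71 | -1.71 | -1.77 |
| 7% | -1.80 | -1.27 | -1.27 | -1.32 | -1.84 |
| 13% | -1.81 | -0.96 | -0.96 | -1.06 | -2.00 |

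Plain imputation repeats the complete-case result. A shift moves the estimate, so it shows how far the result depends on the unseen values. The bias at 1% is 1.79 - 1.71 = 0.08 days.

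**3. The same for a PiMax-like outcome (all assumed).** Take 29% of values below 30 cmH2O and a 5% chance of being missing, raised by a log-odds of 2 below 30. Odds below 30: (0.05/0.95) × e² = 0.389, so the probability is 0.28. Overall missing: 0.29 × 0.28 + 0.71 × 0.05 = 0.117, about 12%. With a lognormal outcome truncated at 100 and imputation by arm, the difference was 5.65 in full data, 5.46 in complete cases and 5.46 after imputation. The loss is 5.65 - 5.46 = 0.19 cmH2O, and 0.19/5.65 = 3%. The usual-care mean was 1.7 cmH2O too high, but most of that cancels between arms.

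**4. Out-of-range weaning values.** The SAP minimum is 0.0833 days. If weaning were imputed untransformed and without bounds at the pilot moments:

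- REDvent: Φ((0.0833 - 2.2)/2.1) = Φ(-1.008) = 0.157
- Usual care: Φ((0.0833 - 4)/2.8) = Φ(-1.399) = 0.081

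In the simulation, 5 to 6% of untransformed draws fell below the minimum, and none did on the log scale.

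**The case against.** The best defence is that this is a conditional sensitivity analysis over very little missing data. The revised protocol allows 1% for attrition or incorrect randomization, no child had withdrawn by August 2019, and fixed rules cover most absent primary outcomes. Death, the main informative loss, is captured by the mortality outcomes and by zero ventilator-free days. All of that stands, and it makes the weaning effect small.

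The simulations also return the complete-case answer partly because they use no auxiliary variables. The SAP does not forbid such variables, and the trial collects rich daily data. That stands too: good auxiliaries would recover part of the bias. Calling MCMC the primary approach also leaves room for others, so a reader who infers that the plan rules out any useful analysis goes too far. The narrower fact remains that no auxiliary variable and no alternative is named.

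A reader might further infer that the plan will impute impossible weaning times. The documents do not support this. They never say weaning is imputed on the raw scale, they allow transformation, and the final ordinal model would place a very low or negative draw in its lowest category, under 0.5 day.

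Finally, PiMax is measured the same way in both arms, and with similar missingness in both the arm difference barely moves. That limits the size of the problem. It does not explain how children extubated after day 28 are to be handled.

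**Conclusion.** The point holds in a limited form. For data judged not missing at random, the stated method does not match its stated purpose. Beyond what unnamed auxiliary variables explain, it will tend to agree with the complete-case result whatever the unseen values are. The outcome to watch is PiMax on the day of extubation, where the design itself creates absent values among slow weaners and the normal model was already found not to fit.

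The size is small where it can be estimated: about 0.08 days for weaning at 1% missing, and 0.19 cmH2O for PiMax. The larger weaning biases at 7% and 13% missing show the mechanism; they do not forecast this trial. These figures rest on assumed missingness mechanisms and, for PiMax, an assumed 12% missing, since the documents give no PiMax missing rate. Nothing here shows that a main result is biased. Severity: minor.

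**What to change.** Split the paragraph by mechanism.

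- **Missing at random.** Impute by fully conditional specification, with predictive mean matching or ordinal models for PiMax and length of weaning. List the imputation variables: arm, the blocking variables and the available auxiliary measures. Earlier daily PiMax can serve for the day-of-extubation value, but not for first-SBT PiMax, because PiMax is not measured in the acute phase.
- **Not missing at random.** Replace plain MCMC with a delta-adjusted imputation, available through the MNAR statement in SAS PROC MI. Shift imputed values towards worse by increasing amounts, separately by arm, rerun the proportional odds model, and report the shift at which the conclusion changes.
- **Reporting.** Give the number of eligible children without a day-of-extubation PiMax by arm, including those extubated after day 28. Label the analysis post hoc, because data cleaning ended in May 2024.

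The cost is SAP wording and a few extra runs, with no new data. The downside is a range of results instead of one.
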